## 9. STATISTICS

### 9.1. *Description of statistical methods*

Demographic and other baseline patient characteristics (age, gender, disease duration, prior and concomitant disease, prior and concomitant therapy) will be compared between therapy groups to demonstrate comparability between groups at baseline using appropriate statistical tests.

Descriptive statistics for data whose distribution follows the law of normal distribution will be presented using the arithmetic mean and standard deviation. For otherwise distributed data descriptive statistics will be presented using non-parametric measures (median/mod, quartiles).

Two-sided confidence intervals will be used to assess treatment efficacy (primary and secondary efficacy criteria).

For primary and secondary efficacy criteria, differences will be considered statistically significant at the p-value level of <0.05.

In accordance with the purpose of the trial, statistical analysis of the results is planned to compare the efficacy of the therapy regimen including Mexidol® in the treatment of attention deficit hyperactivity disorder (ADHD) in children 6-12 years old at different dosing regimens with the efficacy of the regimen including placebo and a combination of the Investigational product and placebo.

The main efficacy criterion is the mean change in the total score on the inattention and hyperactivity/impulsivity subscales of the SNAP-IV scale after 6 weeks of therapy vs. baseline. Descriptive statistics for this indicator will be given and the following statistical hypotheses will be tested:

$$H^0: \mu_p = \mu_T; \\ H^1: \mu_T < \mu_p$$

$\mu_T$  - mean change in SNAP score in the trial group (group 1 Mexidol®, 125 mg OD, or group 2 (Mexidol®, 125 mg BID);

$\mu_p$  - mean change in SNAP score in control group 3 (placebo). The sign " $<$ " is associated with the fact that the change has a negative value.

Comparison of the values of the two groups of patients will be performed by calculating the two-sided 95% confidence interval for the difference of  $\mu_1$  ( $\mu_2$ ) and  $\mu_0$  values. A conclusion on superiority can be made if the upper bound of the two-sided 95% confidence interval for the difference in mean changes in SNAP scores of Mexidol® vs. placebo is negative.

Testing of the null statistical hypothesis can be done using one-factor analysis of variance with Dunnett's posterior criterion and evaluation of contrasts or similar applicable statistical analysis method.

The  $\chi$ -square test or Fisher's exact test will be used to assess differences in event rates.

The  $\chi$ -square test or Fisher's exact test will also be used to assess differences in patient adherence.

Safety parameters will be tabulated for all patients receiving Investigational product/placebo. Comparisons of safety outcomes between trial groups will be made using the  $\chi$ -square or Fisher's exact test (for qualitative data) and the t-test for data whose distribution follows the law

of normal distribution or its non-parametric analogue (for data whose distribution does not follow the law of normal distribution).

A detailed plan for the statistical analysis of the data will be presented in a separate document to be included in the clinical trial report submitted to the regulatory authority.

Deviations from the statistical analysis plan that occur will be described in the clinical trial report.

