##### **Secondary objectives:**

1. To evaluate the efficacy of Mexidol® film-coated tablets 125 mg (PRC PHARMASOFT LLC, Russia) vs. placebo after 6 weeks from the beginning of therapy when administered at a dose of 125 mg OD and 125 mg BID on the basis of the following parameters:
  - a. mean change on the SNAP-IV subscale - inattention;
  - b. mean change on SNAP-IV subscale - hyperactivity/impulsivity
  - c. mean change on the SNAP-IV subscale - oppositional defiant disorder;
  - d. mean change on the SNAP-IV subscale - Conners' clinical index;
  - e. mean change on the Spence Children's Anxiety Scale (SCAS);
  - f. mean change on ADHD Rating Scale-IV value;
  - g. Clinical Global Impressions-ADHD-Severity scale (CGI-ADHD-S);
  - h. assessment of the dynamics of PedMIDAS questionnaire scores (number of days with restriction of daily activity due to headache, number of days with headache, average headache severity and maximum headache severity in scores);
  - i. Clinical Global Impressions Scale - Improvement (CGI-I).
2. To evaluate the safety of Mexidol® film-coated tablets, 125 mg (RPC PHARMASOFT LLC, Russia) vs. placebo based on the assessment of frequency, severity and nature of adverse events.

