**Secondary efficacy criteria:**

1. mean change on the SNAP-IV inattention subscale after 6 weeks of therapy vs. baseline;
2. mean change on SNAP-IV subscale hyperactivity/impulsivity after 6 weeks of therapy vs. baseline;
3. mean change on the SNAP-IV subscale, oppositional defiant disorder, after 6 weeks of therapy vs. baseline;
4. mean change in SNAP-IV subscale - Conners index after 6 weeks of therapy vs. baseline;
5. mean change on the Spence children's anxiety scale (SCAS) after 6 weeks of therapy vs. baseline;
6. mean change on ADHD Rating Scale-IV scores after 6 weeks of therapy vs. baseline;
7. clinical Global Impressions-ADHD-Severity (CGI-ADHD-S) scale score after 6 weeks of therapy vs. baseline;
8. assessment of the dynamics of PedMIDAS questionnaire scores (number of days with restriction of daily activity due to headache, number of days with headache, average headache severity and maximum headache severity in scores);
9. Clinical Global Impressions Scale - Improvement (CGI-I) score after 6 weeks of therapy vs. baseline.

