#### **4.6.7. Completion of questionnaires**

The SNAP-IV, SCAS, ADHD Rating Scale IV questionnaires, child/adolescent headache examination charts, and PedMIDAS questionnaires are completed by the investigator from the patient's parents at the trial visits (Table 1.2). The questionnaires should be assessed by the same parent throughout the trial. The Child/Adolescent Headache Assessment Card and PedMIDAS questionnaire are completed only if the patient has headache complaints identified at Visit 2; scale data are completed at Visit 2 for the past 3 months, at Visit 5 for the past 1.5 months (6 weeks).

The CGI-ADHD-S, CGI-I scales are assessed by the investigator. These scales are scored and completed by the same researcher who made the original measurements.

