### **9.3. *Applied significance level***

The plan is to apply a significance level of 0.05 and calculate a two-sided 95% confidence interval.

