- **Various assessments for treatment success:** secondary efficacy endpoints were planned to support the results of the primary efficacy analysis using the t-test - for data whose distribution conforms to the law of normal distribution, or the Mann-Whitney U-test for data whose distribution does not conform to the law of normal distribution.
- **Missing data:** analyses of full cases and post-hoc analyses using the last observation carry forward method (LOCF) to assess consistency of results are assumed.

The feasibility of using a number of statistical methods will be assessed after data collection has been completed, as the nature of the data distribution, sample homogeneity, etc. is not known in advance. During the course of the analysis, the list of methods to be used may be modified and supplemented if necessary for the qualitative processing of the data.

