## Plan for statistical analysis of efficacy and safety parameters

Table 4. Statistical analysis of secondary, endpoints (SNAP-GU, CGI-ADHD-S, SCAS, PedMIDAS and ADHD Rating Scale IV) (template)

Indicator 	Mexidol®				Placebo				Mexidol®+ Placebo			
	Visit 2 (Day 1)	Visit 5 (Day 43+1)	Dynamics		Visit 2 (Day 1)	Visit 5 (Day 43+1)	Dynamics		Visit 2 (Day 1)	Visit 5 (Day 43+1)	Dynamics	
			Abs.	%			Abs.	%			Abs.	%
N												
Mean												
95% CI, L												
95% CI, U												
Median												
Min												
Max												
Q 1												
Q 3												
Range												
QRange												
SD												
CV												
Intragroup comparison: comparison of data at the end of therapy with data at the start of therapy (statistical criterion  ) (p-level value)												
Comparison of drugs (statistical test  ) (p-value)												
Indicator span diagram/ indicator scatter diagram												

 - SNAP-IV subscale score - "inattention."

- SNAP-IV subscale score - "hyperactivity/impulsivity."

- SNAP-IV subscale score - oppositional defiant disorder;

- SNAP-IV subscale score - Conners index;

Clinical Global Impressions-ADHD-Severity scale (CGI-ADHD-S).

- Spence children's anxiety scale (SCAS) scores after 6 weeks of therapy compared to baseline;

PedMIDAS questionnaire score

- ADHD Rating Scale-IV score after 6 weeks of therapy compared with baseline.

 T-test for related samples or Wilcoxon test depending on the type of distribution of the indicator T-test for independent samples or Mann-Whitney test depending on the type of distribution of the indicator**Version 1.0 of 27.9.2019**Protocol-specific version for protocol #PHS-ADHD-002-MEX- TAB,  
version 3.0 dated 19.07.2019.**CONFIDENTIAL**

page 33 of 42

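### Eighteen to 24 secondary tests are each called significant at p<0.05, for either dose, with no gate on the primary, no order and no adjustment.

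*Protocol*

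**What the plan says.** Protocol 9.1 states: "For primary and secondary efficacy criteria, differences will be considered statistically significant at the p-value level of <0.05". The same sentence stands in the statistical methods part of the synopsis (Protocol 1.1) and in SAP 6. Protocol 9.3 fixes the level and the sidedness: "The plan is to apply a significance level of 0.05 and calculate a two-sided 95% confidence interval".

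The secondary objectives (Protocol 3.2) cover both regimens: "when administered at a dose of 125 mg OD and 125 mg BID on the basis of the following parameters". Protocol 4.1 lists nine numbered secondary criteria. The eighth, PedMIDAS, has four components: "number of days with restriction of daily activity due to headache, number of days with headache, average headache severity and maximum headache severity in scores". PedMIDAS is collected only in a subset, because the headache card and "PedMIDAS questionnaire are completed only if the patient has headache complaints identified at Visit 2" (Protocol 4.6.7).

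The footnotes to SAP Tables 4 and 5, the templates for the secondary endpoints, name the between-group test: "T-test for independent samples or Mann-Whitney test depending on the type of distribution of the indicator". The only multiplicity method in either document is Dunnett's. It is attached to the SNAP primary hypothesis and offered as one option (Protocol 9.1, SAP 7).

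On the role of the secondaries, SAP 6 says that "secondary efficacy endpoints were planned to support the results of the primary efficacy analysis using the t-test" or, for non-normal data, the Mann-Whitney test. The written superiority rule concerns the SNAP difference only.

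**The concern.** The rule does more than describe the data. It tells the report's author to label any secondary difference below 0.05 as statistically significant, at each dose, and no text withdraws that label when the dose has missed its primary criterion. Anxiety (SCAS), oppositional behaviour and headache are distinct from the primary score, so a chance finding on one of them could read as a benefit in its own right. SAP 2 sends the results of the planned analysis as a whole to the registration dossier and to publications.

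This is separate from the multiplicity of the two primary comparisons. Making Dunnett mandatory for the primary would leave the secondary rule as it is.

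**Working it through.** **No stated figure to reproduce.** The documents give no familywise error rate for the secondaries. The sample size concerns only the primary: 2 x 6.27² x (1.96 + 0.842)² / 2.5² is about 99 per group, and with the t distribution 100 per group gives 80.1% power, in line with the stated 100. It does not bear on this point.

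**Count.** By numbered criterion: 9 x 2 doses = 18 tests. By variable: 8 single-score criteria + 4 PedMIDAS scores = 12, and 12 x 2 = 24 tests. The per-protocol repeat and the within-group tests would add more p-values and are left out.

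**Independence, as an upper reference.** The chance of at least one p<0.05 is 1 - 0.95^k: 60.3% for k = 18 and 70.8% for k = 24. Counting only results that favour the drug (0.025 per test), 1 - 0.975^k gives 36.6% and 45.5%.

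**With correlation.** The tests are not independent. Both doses share one placebo group, and the scales overlap. A simulation (200,000 draws) used these assumptions: no drug effect on any endpoint, three equal arms, a shared placebo group (correlation 0.5 between the two dose contrasts), exchangeable correlation rho between endpoints, and critical value 1.96. For the last row of each block the primary was added as one more endpoint with the same rho. The values of rho are assumptions.

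| Event | rho 0 | rho 0.3 | rho 0.5 | rho 0.7 |
|---|---|---|---|---|
| 18 tests: any p<0.05 | 58% | 52% | 44% | 34% |
| 18 tests: any favouring Mexidol | 34% | 27% | 23% | 17% |
| 18 tests: a dose fails its primary but has a favourable significant secondary | 33% | 26% | 20% | 14% |
| 24 tests: any p<0.05 | 68% | 61% | 51% | 39% |
| 24 tests: any favouring Mexidol | 43% | 33% | 26% | 20% |
| 24 tests: a dose fails its primary but has a favourable significant secondary | 42% | 31% | 24% | 17% |

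The third row of each block counts the event at either dose. For one given dose, with 12 variables, it is 26%, 14% and 10% at rho 0, 0.5 and 0.7.

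**Sensitivity.** At rho 0.9, 24 tests still give 23% in either direction and 12% favouring Mexidol. If the endpoints form two unrelated clusters (eight ADHD, behaviour and anxiety scores; four headache scores) with correlation 0.7 inside each, the figures are 48% and 26%. High agreement among the ADHD scales alone therefore does not remove the problem.

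**With a gate.** If a secondary may be claimed for a dose only after that dose has met its primary, failing the primary and still claiming a secondary is impossible by construction. In the same model the chance of any false favourable secondary claim falls to about 1-4% across rho 0 to 0.7, before any fixed order is added.

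**The case against.** The strongest reply is that the secondaries are already subordinate. SAP 6 places them among the sensitivity analyses, as support for the primary. The superiority rule is written for SNAP only, and the yes/no entry for superiority appears only in SAP Table 6, the primary endpoint table. No text provides for an efficacy conclusion from a secondary alone. This stands, and it limits the harm. A reader might infer that the plan lets efficacy be declared on a secondary whatever the primary shows, and the documents do not say that. But a supportive role is not a decision rule, and the significance label in three places is one.

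Two further points stand in part. First, a count of 24 should not be taken as the plan's own. The plan numbers nine criteria, SAP Table 4 lists PedMIDAS as a single questionnaire score, and PedMIDAS is collected only in children with headache. The range 18 to 24 is the fair statement. Second, zero correlation is implausible. Most scales are completed through the same parent and the CGI scales by the same investigator (Protocol 4.6.7), and inattention and hyperactivity/impulsivity are the two parts of the primary sum. The figures at rho 0 and under independence are bounds, not estimates.

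**Conclusion.** The point holds. The plan calls every secondary difference at either dose statistically significant at p<0.05, with no gate, order or adjustment. With no drug effect and assumed correlations of 0.3 to 0.7, over 18 to 24 tests:

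- at least one p<0.05 in either direction: about 34-61%;
- at least one result falsely favouring Mexidol: about 17-33%;
- a dose that fails its primary but shows a favourable significant secondary: about 14-31%.

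A reader might infer that a false claim of benefit is likely. The figures do not support that: the chance is below even odds in every case examined, including independence (45.5%). Only the either-direction figure passes one half, and it includes results against the drug. The sizes rest on the assumed correlations, on normal theory, and on every child contributing to every endpoint, which is not so for PedMIDAS. The primary conclusion is unaffected, so this is a change that should be made rather than one on which the trial's main result depends.

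**What to change.** Change the sentence in all three places (Protocol 1.1, Protocol 9.1 and SAP 6). Altering only some of them would leave the documents in contradiction. Suggested content:

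- A secondary difference may be called statistically significant for a dose only if that dose has met its primary criterion.
- Testing for that dose then follows one fixed order, written in the SAP before unblinding, and stops at the first failure. The numbered order in Protocol 4.1 would serve as an example. The SAP should also say how the four PedMIDAS scores enter, because a failure in the headache subset at position 8 would block CGI-I at position 9.
- All other secondary results are reported as supportive estimates with 95% confidence intervals and nominal p-values, without a claim of significance.

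The gate inherits the primary's error rate. With two unadjusted primary comparisons that rate is 9.1% (two-sided, shared placebo), so 5% control across both doses also needs the two primary comparisons to be adjusted and the adjusted level carried down each dose's sequence. A split of 0.05/2 = 0.025 per dose would do this.

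The cost is wording only: no patients, visits or data. The downside is that fewer secondary results may be called significant.

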superiority can be made if the upper bound of the two-sided 95% confidence interval for the difference in mean changes in SNAP scores of Mexidol® vs. placebo is negative.

For primary and secondary efficacy criteria, differences will be considered statistically significant at the p-value level of <0.05.

The  $\chi$ -square test or Fisher's exact test will be used to assess differences in event rates.

The  $\chi$ -square test or Fisher's exact test will also be used to assess differences in patient adherence.

Safety parameters will be tabulated for all patients who received investigational medicinal product. Comparisons of safety profiles between trial groups will be made using the  $\chi$ -square test (for qualitative data) and the t-test for data whose distribution follows the law of normal distribution, or its non-parametric analogue (for data whose distribution does not follow the law of normal distribution).

AEs will be coded per MedDRA and categorised using Organ System Classes and preferred term. The protocol provides for the recording of all AEs that occur to the patient after the first administration of the trial therapy and until the end of the patient's participation in the trial.

During screening, information about medical adverse events will be attributed to the patient's medical history (pre-existing/concomitant conditions).

The planned trial will record all deviations in the health status of patients (based on the results of physical examination, laboratory and instrumental methods of investigation) from the data obtained at the Screening and from the accepted reference values.

After obtaining the necessary information, the investigating physician will categorise the patient's condition as 'normal', 'clinically insignificant abnormalities' or 'clinically significant abnormalities'. In case the abnormalities detected during the trial have not been previously reported, or there is an aggravation of the patient's condition vs. the data obtained at Screening, the detected abnormalities will be classified as AEs.

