**Plan for statistical analysis of efficacy and safety parameters**

1. To evaluate the efficacy of Mexidol® film-coated tablets, 125 mg (RPC PHARMASOFT LLC, Russia) vs. placebo after 6 weeks from the beginning of therapy in relation to the average change in the total score on the "inattention" and "hyperactivity/impulsivity" subscales of the SNAP-IV scale when administered at a dose of 125 mg OD.
2. To evaluate the efficacy of Mexidol® film-coated tablets, 125 mg (RPC PHARMASOFT LLC, Russia) vs. placebo after 6 weeks from the beginning of therapy in relation to the average change in the total score on the "inattention" and "hyperactivity/impulsivity" subscales of the SNAP-IV scale when administered at a dose of 125 mg BID.

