## Plan for statistical analysis of efficacy and safety parameters

Table 3. Statistical analysis of the primary endpoint (template)

Total score on the "inattention" and "hyperactivity/impulsivity" subscales of the SNAP IV scale	Mexidol®				Placebo				Mexidol®+ Placebo			
	Visit 2 (Day 1)	Visit 5 (Day 43+1)	Dynamics		Visit 2 (Day 1)	Visit 5 (Day 43+1)	Dynamics		Visit 2 (Day 1)	Visit 5 (Day 43+1)	Dynamics	
			Abs.	%			Abs.	%			Abs.	%
N												
Mean												
95% CI, L												
95% CI, U												
Median												
Min												
Max												
Q 1												
Q 3												
Range												
Q Range												
SD												
CV												
Intragroup comparison: comparison of data at the end of therapy with data at the start of therapy (statistical criterion  ) (p-level value)												
Comparison of drugs (statistical test  ) (p-value)												
Indicator span diagram/ indicator scatter diagram												

 T-test for related samples or Wilcoxon test depending on the type of distribution of the indicator T-test for independent samples or Mann-Whitney test depending on the type of distribution of the indicator

Version 1.0 of 27.9.2019

Protocol-specific version for protocol #PHS-ADHD-002-MEX- TAB,  
version 3.0 dated 19.07.2019.

CONFIDENTIAL

page 32 of 42

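### Two primary dose-vs-placebo comparisons, with Dunnett only optional and not tied to the 95% CI rule: if either dose may win, the false-claim risk is about 4.5% one-sided, and Dunnett-adjusted power is about 67–72% per dose

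*Protocol*

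**What the plan says.** Protocol 3.2 and SAP 1 list two primary objectives. The first ends "SNAP-IV scale when administered at a dose of 125 mg OD"; the second is the same for twice daily. Protocol 9.1 defines the tested mean as "mean change in SNAP score in the trial group (group 1 Mexidol®, 125 mg OD, or group 2" (twice daily).

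The decision rule is: "A conclusion on superiority can be made if the upper bound of the two-sided 95% confidence interval for the difference in mean changes" is negative. It appears in Protocol 1.1 and 9.1 and in SAP 6 and 7, each time without the word simultaneous or adjusted. Protocol 9.3 adds only "The plan is to apply a significance level of 0.05 and calculate a two-sided 95% confidence interval".

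Dunnett is named in two places, Protocol 9.1 and SAP 7, in the same permissive sentence: "Testing of the null statistical hypothesis can be done using one-factor analysis of variance with Dunnett's posterior criterion and evaluation of contrasts or similar" applicable methods. Protocol 1.1, Protocol 9.3 and SAP 6 name no multiplicity method.

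SAP Table 3, the template for the primary endpoint, footnotes the between-group comparison as "T-test for independent samples or Mann-Whitney test depending on the type of distribution of the indicator". SAP 6 and SAP 9 add that during the analysis "the list of methods to be used may be modified and supplemented". SAP Table 6, which records whether superiority is proven, has columns for twice daily vs once daily and twice daily vs placebo, but none for once daily vs placebo.

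The sample size (Protocol 9.2, SAP 8) uses one-sided 0.025, at least 80% power and a 2.5-point difference for one active group against placebo.

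**The concern.** An analyst can follow this plan and report two ordinary 95% intervals, or two Dunnett intervals, and arguably depart from nothing in either case. The choice sits inside the primary decision rule. With ordinary intervals and an either-dose claim, the error across the two doses exceeds the 2.5% that the plan applies to one test. With Dunnett, the error is held but the stated 80% no longer describes the power for a given dose. SAP 1 calls this a phase II–III trial, and SAP 2 says the results will go into a registration dossier, so the rule should be settled before anyone sees results by arm.

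**Working it through.** **Inputs** (Protocol 9.2, SAP 8): difference 2.5 points; SD of change 4.70 on placebo and 7.515 on Mexidol; one-sided 0.025; power 80%; 100 completers per arm; 1:1:1 allocation.

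**1. Reproduce the plan's figure.**
- Two-group pooled SD = √((4.70² + 7.515²)/2) = 6.268, the plan's 6.27.
- n = 2 × 6.268² × (1.96 + 0.8416)² / 2.5² = 98.7 per arm. By the two-sample t-test, power is 79.7% at 99 and 80.1% at 100.

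The stated 100 is therefore right for one unadjusted comparison, with no allowance for the second dose.

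**2. Chance of at least one false claim, no adjustment.** The comparisons share the placebo arm, so with equal SDs their correlation is 0.5. The chance is 1 − Φ₂(1.96, 1.96; 0.5) = 4.54% one-sided (4.5% by t-based simulation). With the plan's SDs the correlation is 4.70²/(4.70² + 7.515²) = 0.28, and the result depends on the error term:
- two-group tests: 4.8%;
- three-arm pooled SD, √((4.70² + 2 × 7.515²)/3) = 6.71: 3.5%.

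**3. Power with 100 per arm when both doses have the 2.5-point effect** (simulation). The single-step Dunnett critical value is about 2.22 on 297 df, against 1.968 unadjusted.

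| Method and SDs | Per dose | At least one | Both |
|---|---|---|---|
| Unadjusted, common SD 6.27 | 80% | 91% | 69% |
| Unadjusted, plan's SDs, two-group tests | 80% | 94% | 67% |
| Unadjusted, plan's SDs, three-arm pooled | 76% | 91% | 61% |
| Dunnett, common SD 6.27 | 72.5% | 86% | 59% |
| Dunnett, plan's SDs, three-arm pooled | 67% | 85% | 49% |

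Hand check of the last row, per dose:
- The true standard error of the difference is √((4.70² + 7.515²)/100) = 0.886.
- The pooled analysis uses 6.709 × √(2/100) = 0.949, so a win needs an observed difference of about 2.222 × 0.949 = 2.11.
- Φ((2.5 − 2.11)/0.886) = Φ(0.44) = 67%.

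Dunnett holds the false-claim rate at 2.5% with equal SDs and at about 1.8% with the plan's SDs and a pooled error term. If only one dose works, its power for at least one win is about 73% (67% with the plan's SDs, pooled).

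**4. How often the choice matters.** At SD 6.268 the interval half-widths are 1.968 × 6.268 × √(2/100) = 1.74 and 2.222 × 6.268 × √(2/100) = 1.97. An observed advantage between 1.74 and 1.97 points wins unadjusted and fails under Dunnett. With a common SD and both doses effective, at least one dose's verdict changes in about 15% of trials. The verdict for any dose changes in about 5% if both work, 8% if one works and 2% if neither does.

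**The case against.** The strongest reply is that Dunnett is named, and that a method similar to ANOVA with Dunnett most naturally means another many-to-one procedure. On that view Table 3 is a largely descriptive template, and the superiority verdict belongs to Table 6, where the test is left blank. There are also safeguards: the SAP is approved before database cut-off (Protocol 9.6), codes are disclosed as a whole only after the database is closed (Protocol 4.9), and deviations are reported (SAP 9).

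This deserves weight. A reader might infer that the plan ignores multiplicity, and the documents do not support that. But Dunnett is attached to testing the null hypothesis and not to the interval that decides superiority, and the only between-group test named for the primary table is an unadjusted one. Reporting deviations does not help when both choices can be read as compliant.

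A second reply is that both doses may be meant to win. Then no adjustment is needed and the 4.5% does not apply. Neither document says so, however, and power for both would be only about 61–69% unadjusted.

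A third is that single-step Dunnett is not the most powerful choice under the plan's SDs. Bonferroni on two-group tests gives about 71% per dose and 88% for at least one. That is fair: the need is for one binding method, and Dunnett is simply the one already named.

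**Conclusion.** The point stands. As written, the decision rule does not hold 2.5% across the two primary comparisons if either dose can support a claim. That reading is inferred from the two separate objectives and the either-group definition of the tested mean; it is not stated. Under it, the false-claim probability is about 4.5% one-sided with equal SDs and 3.5–4.8% with the plan's SDs. Adjusted power under single-step Dunnett is about 67–72% per dose and 85–86% for at least one dose if both work. The lower figures use the plan's SDs with a three-arm pooled error term, and the higher ones a common SD of 6.27. All assume 100 evaluable children per arm.

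Two stronger readings do not hold. A reader might infer that the trial misses its power target and must be enlarged. The target is missed for each dose separately, but it is met for at least one dose when both work, and the documents do not say which is meant. A reader might also take 72% as the adjusted per-dose power. The named one-factor ANOVA with the plan's own SDs gives 67%, so the range should be stated.

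This should be fixed before unblinding. It concerns the primary decision rule, and the correction is cheap.

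**What to change.** 1. In Protocol 1.1 and 9.1 and SAP 6 and 7, make one multiplicity method binding and tie it to the decision rule. The simplest wording is that superiority of a dose is concluded if the upper bound of its Dunnett simultaneous two-sided 95% interval against placebo, for the difference in mean change, is below 0. In Protocol 9.1 and SAP 7, turn the permissive verb into a binding one and delete the allowance for a similar method. Exempt the primary test from the clauses in SAP 6 and 9 that let methods be modified. A pre-specified step-down Dunnett or fixed-order test is an acceptable alternative if chosen before unblinding.
2. State that footnote 2 of SAP Table 3 does not decide the primary between-group comparison. Keep any Mann-Whitney analysis as a sensitivity analysis, so that a route for non-normal data remains.
3. In Protocol 9.2 and SAP 8, say that 80% refers to one unadjusted comparison. Give adjusted power as about 67–72% per dose and 85–86% for at least one dose if both work, naming the SD assumption.
4. In SAP Table 6, add the missing once-daily vs placebo column. Keep twice daily vs once daily, since Protocol 9.1 and SAP 7 plan a comparison with the product-plus-placebo arm, but label it as outside the error-controlled primary family.
5. SAP 1.0 was written for Protocol 3.0, and the protocol is now 4.0. Align the two in the same revision.

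The cost is wording and two table templates, with no extra patients. The downside is that the stated per-dose power falls below the plan's 80% minimum.
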